6.3 Statistical Methods

6.3.1 Overview

All data analyses will be preceded by extensive data checking and verification to resolve the reasons for missing values, inconsistencies, and out-of-expected-range values. All statistical estimates of population parameters will be tabulated along with corresponding confidence intervals (CIs) and will be based on the convenience sample of patients participating in the study. The primary focus of the analyses will be the magnitudes and directions of the point- and interval-estimates. All analyses will be in intention-to-treat analyses. All reported p-values will be 2-sided; <0.05 representing significance. All hypothesis test results (i.e. p-values) that are deemed not statistically significant (defined by a p-value \geq 0.5) will be reported as inconclusive. Analyses will be performed with SAS 9.4 (Cary, NC) or a comparable statistical programming software package.

6.3.2 Missing data

All attempts will be made to keep missing data to a minimum, and participants who withdraw from treatment will be encouraged to continue on study in order to provide complete follow-up information. Thus, irrespective of withdrawal from treatment, all participants should continue to be followed with all relevant, scheduled outcome evaluations until the end of the study. The characteristics at the time of study start for those participants without complete follow-up will be examined; however, there will be limited statistical power to detect any but major differences between these participants and those with complete follow-up. Missing data variables will be identified in the data management system with a missing data indicator such that they can be easily identified. Reasons for missing data will be captured at each study visit and entered into the study database. No imputation of missing data will be performed.

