1.3.1. Risks

Risks of furosemide include electrolyte abnormalities (hypokalemia, hypomagnesemia, and hypocalcemia), hypotension, allergic or toxicity-related symptoms (rash, tinnitus, and hearing change), and other symptoms (cramps, dizziness, unusual tiredness/weakness, chest pain, nausea, vomiting, diarrhea, and numbness/tingling). Furosemide-induced ototoxicity can lead to transient or permanent deafness. Ototoxicity primarily occurs with high-dose intravenous therapy (e.g. >240 mg/hr infusions) or at lower doses in patients with kidney function impairment or concurrent use of other ototoxins such as aminoglycosides.

We have chosen our study selection criteria to exclude patients who are at increased risk for furosemide side effects including those with frequent hypotension, cirrhosis, a hearing disorder, or electrolyte abnormalities in the prior 30 days (hypokalemia defined as serum potassium <3.5 mEq/L, hypomagnesemia, defined as serum magnesium <1 mg/dL, and hypocalcemia, defined as serum corrected calcium < 8 mg/dL), and those taking an interacting drug or substance including an aminoglycoside, cisplatin, methotrexate, cyclosporine, adrenocorticotropic hormone (ACTH), lithium, phenytoin, oral/intravenous steroid, or natural licorice.

In the current trial, risks related to furosemide will be reduced through close monitoring of serum electrolytes, patient symptoms (including hearing), BP, and serum and urine furosemide levels. In addition, we will withdraw participants from the study if any of the following occurs during the course of the study: 1) pregnancy; 2) initiation of a non-loop diuretic (spironolactone, eplerenone, ethacrynic acid, thiazides); 3) initiation of an interacting drug (aminoglycoside, methotrexate, cyclosporine, ACTH, lithium, phenytoin, or oral/intravenous steroid); and/or 4) new diagnosis of cirrhosis.

Occurrence of any of the following events will end dose up-titration (defined below): 1) electrolyte abnormalities, 2) side effects attributable to furosemide (e.g. hypotension, allergic or toxicity-related symptoms), and/or 3) patient non-acceptance. If one of these events occur, the participant will return to the prior tolerated furosemide dose. If one of these events occurs at the lowest administered dose, furosemide will be stopped and not re-started.

- Serum potassium <3.2 mEq/L
- Serum magnesium <0.8 mEq/L
- Serum corrected calcium <7.0 mg/dL

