3.5.5 Concomitant therapy

Medication use (both oral and intravenous) will be collected at baseline and throughout the course of the study. Nonloop diuretic (e.g. spironolactone, eplerenone, ethacrynic acid, thiazides), aminoglycoside, cisplatin, methotrexate, cyclosporine, ACTH, lithium, phenytoin, and oral/intravenous steroid use are exclusion criteria. If these medications are initiated during follow-up the treating clinician will be contacted by the research team. If the prohibited drug cannot be discontinued, study medication will be withdrawn, and participants will continue to be followed.

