4.5 Participant Completion/ Withdrawal procedures

If a participant withdraws from the study before Week 18, an early withdrawal visit will be scheduled to conduct the week 18 assessments (24-hour urine, symptom assessment, hearing assessment, acceptance assessment, pill count, and return of study drug). Patients who stop taking study medication are not considered early withdrawals and will be asked to continue to provide follow-up data on the study schedule and to participate in the final study visit at week 18.

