Serum blood tests: The following tests will be assessed via blood samples: sodium, potassium, chloride, urea, creatinine, magnesium, calcium, albumin and serum furosemide level. An additional 2.5 mL blood sample will be drawn, frozen, and stored in UNC Kidney Center -80° freezers for future testing as needed. Blood samples will be collected via the vascular access by trained dialysis clinic personnel.

24-hour urine collection: The following tests will be assessed via 24-hour urine collections: urine volume, sodium, urea, creatinine, and urine furosemide level. An aliquot of urine will be taken from the sample after the before-listed measurements are performed and be frozen and stored in UNC Kidney Center -80° freezers for future testing as needed. Urine samples will be collected by the patient in 24-hour urine collection containers. Containers will be provided by and returned to study staff at the dialysis clinic at specified study visits.

Symptom assessment: Study staff will administer a symptom questionnaire (*Appendix, Section 13.1*) to participants at specified study visits.

Hearing assessment: Study staff will administer the Inner Ear instrument (*Appendix, Section 13.2*) to participants at specified study visits.

Pill counts: Study staff will perform pill counts at specified study visits.

Acceptance assessment: Study staff will ask participants the following yes/no/unsure question: "If recommended, would you be willing to stay on the dose of furosemide you have received during the last week?"

Clinical data: The following data will be obtained from the EHR: HD treatment BPs (systolic and diastolic), weights (preand post-HD), UF volumes/rates, dialysate composition (sodium, potassium, bicarbonate, calcium), dialysate and blood flow rates, and vascular access type.

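### With no imputation, no stated denominator and no missing-outcome sensitivity analysis, the binary primary rates become available-case rates, and acceptability is the one most clearly tilted upward

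*Combined protocol and SAP*

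**What the plan says.** Section 6.3.1 states: "All analyses will be in intention-to-treat analyses". Section 6.3.2 states: "No imputation of missing data will be performed". Section 6.1 defines the primary urine-response, acceptability and adherence endpoints as incidences, and Section 6.3.4 sends categorical outcomes to generalized estimating equations (GEE). No section says who forms the denominator of an incidence or how a treated participant without a value is counted.

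The plan does try to limit missing data. Section 6.3.2 says that "irrespective of withdrawal from treatment, all participants should continue to be followed with all relevant, scheduled outcome evaluations until the end of the study". Section 4.5 adds: "Patients who stop taking study medication are not considered early withdrawals and will be asked to continue to provide follow-up data". For those who leave the study, "an early withdrawal visit will be scheduled to conduct the week 18 assessments", and these include the 24-hour urine and the acceptance question. Section 6.3.2 also records reasons for missing data and compares baseline characteristics. Section 6.2 reports withdrawals and non-continuation to period 2 as exploratory counts.

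The acceptance question in Section 5.1 asks "would you be willing to stay on the dose of furosemide you have received during the last week", with yes, no or unsure as answers. Section 4.4 schedules it weekly in weeks 1 to 6 and every two weeks from week 8 to week 18. Under Section 3.5.2, unwillingness to take the drug ends up-titration, and at the lowest dose it ends treatment for good.

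**The concern.** A rule against imputation, without a rule for the denominator, leaves the software to decide. GEE uses the observations that exist. In its unweighted form it generally needs data missing completely at random, and the plan states neither weighting nor working correlation. The intention-to-treat label is therefore not made operational for the binary endpoints.

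For acceptability, the missing values are linked to the outcome. A participant who stops through unwillingness has no later answer that fits the question as worded, so longer-term acceptability will rest mainly on people still taking the drug.

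Section 6.3.1 puts the weight of the analysis on the size and direction of estimates, and Section 6.4 wants the data to inform a later randomized trial. A rate whose denominator shrinks as people refuse or leave is a poor guide for either purpose.

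**Working it through.** **The plan's own figure.** Section 6.4 gives 83% power for a mean change of 5 mL/24-h with N = 36, SD 10 and two-sided alpha 0.05. A one-sample t-test has noncentrality (5/10) × √36 = 3.0, which gives 83.1%, so the figure reproduces. It concerns a mean in mL and has no bearing on how the binary rates are counted.

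**Where values can go missing**
- *Acceptance:* the question presupposes drug in the last week (Section 5.1), and refusal at the lowest dose ends treatment (Section 3.5.2). A no may be recorded around the time of stopping, but no section says which visit defines the endpoint or that the no carries forward.
- *Urine:* period 1 has one collection after baseline, at week 5 (Section 4.1). One unreturned container removes a participant from short-term efficacy. Section 9.1 pays more for returned samples, so non-return is foreseen.
- *Pill counts:* Section 3.5.11 foresees containers that are not returned.
- *Exits:* Section 9.2.1 lists withdrawal of consent, transfer to another clinic and termination for not following data collection procedures. For a prohibited drug started during the study, Section 1.3.1 says "we will withdraw participants from the study if any of the following occurs during the course of the study", whereas Section 3.5.5 says "study medication will be withdrawn, and participants will continue to be followed" if that drug cannot be stopped.
- *Period 2:* only participants who tolerated and accepted the drug continue it (Section 3.5.2), and more are recruited if fewer than 30 are eligible (Section 6.4).

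**Size.** N = 36 and N = 40 come from Section 6.4. The number missing, m, and the observed rate are assumptions, since the documents give neither. With x successes among N − m observed, the observed rate is x/(N − m), missing-as-failure is x/N, and missing-as-success is (x + m)/N. Intervals are 95% Clopper-Pearson.

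| N | m | Observed | Missing as failure | Missing as success | Gap, observed minus failure |
|---|---|---|---|---|---|
| 36 | 2 | 14/34 = 41.2% (24.6–59.3) | 14/36 = 38.9% (23.1–56.5) | 16/36 = 44.4% | 2.3 points |
| 36 | 2 | 20/34 = 58.8% (40.7–75.4) | 20/36 = 55.6% (38.1–72.1) | 22/36 = 61.1% | 3.3 points |
| 36 | 6 | 18/30 = 60.0% (40.6–77.3) | 18/36 = 50.0% (32.9–67.1) | 24/36 = 66.7% | 10 points |
| 40 | 10 | 18/30 = 60.0% (40.6–77.3) | 18/40 = 45.0% (29.3–61.5) | 28/40 = 70.0% | 15 points |
| 40 | 10 | 24/30 = 80.0% (61.4–92.3) | 24/40 = 60.0% (43.3–75.1) | 34/40 = 85.0% | 20 points |

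The gap equals the observed rate × m/N. It runs from 0.40 × 2/36 = 2.2 points to 0.80 × 10/40 = 20 points.

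**Direction.** Bias = (observed rate − rate among the missing) × m/N. Take an observed rate of 60%:

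| Rate among the missing | 2 of 36 missing | 6 of 36 missing | 10 of 40 missing |
|---|---|---|---|
| 0% | +3.3 | +10.0 | +15.0 |
| 30% | +1.7 | +5.0 | +7.5 |
| 60% | 0 | 0 | 0 |
| 80% | −1.1 | −3.3 | −5.0 |

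For acceptance, people who stopped because they were unwilling belong near the 0% row. For urine, nothing in the documents fixes the row.

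**The case against.** A reader might infer that everyone who stops furosemide drops out of the efficacy rate. The documents do not support that. Sections 4.5 and 6.3.2 keep such participants in follow-up, and off-drug urine counts under intention-to-treat. Those who leave the study are offered a urine collection. Only a participant who gives no urine at all is lost.

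A reader might also infer that urine response must be overstated. That does not follow either. Titration ends for low electrolytes, rash, hearing change, hypotension put down to hypovolemia, or refusal. None of these is defined by a weak urine response, and hypovolemia could accompany a strong one.

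On acceptability, the question is asked repeatedly, so most people who stop later will have earlier on-drug answers, and refusal is recorded as an event in its own right. That narrows the problem to visits after stopping, but it leaves open which answer counts. The withdrawal counts in Section 6.2 help a reader judge the effect, yet they stand apart from the primary rates. Section 6.3.2 itself concedes that the baseline comparison has little power.

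Two further objections stand. Intention-to-treat without imputation is not a contradiction in a single-arm pilot. And Section 6.4 does not say that the binary rates will size the later trial.

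**Conclusion.** The gap is real and worth closing. As written, the binary primary rates will be available-case rates, and none of the planned sensitivity analyses shows how much that matters. Upward tilt is well supported for acceptability, above all in the longer term, because refusal leads to stopping and stopping leaves the question without a valid answer. Period 2 adds to it, since eligibility depends on tolerance and acceptance and the group is topped up. For urine response the direction of bias is unknown.

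The difference of about 2 to 20 points between the observed and missing-as-failure rates rests on assumed observed rates of 40% to 80% and 2 to 10 missing out of 36 or 40. It is a range of sensitivity, not an estimate of bias. The fall from 36 participants to 30 in Section 6.4 concerns period 2 eligibility and should not be read as a forecast of missing urine.

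**What to change.** 1. In Section 6.3.2, set the denominator of the binary acceptability and efficacy endpoints to all participants who took a dose. Show those recruited to top up period 2 separately.
2. Count participants who stopped for refusal or intolerance and have no valid later acceptance answer as not accepting. State which visit defines the endpoint and how an unsure answer is counted.
3. Keep observed off-drug urine values as they are, and assign the early-withdrawal urine to a stated time point.
4. In Section 6.3.7, add missing-as-failure and best-case and worst-case bounds for missing urine, acceptance and pill-count values, with the observed-data rate alongside.
5. Reconcile Sections 1.3.1 and 3.5.5 on whether follow-up continues after a prohibited drug is started.

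The cost is SAP wording and a few table rows, with no new data collection. Headline rates may come out lower. Missing-as-failure mixes response with retention, which is why it belongs beside the observed urine rate and should not replace it.

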6.3.3 Descriptive analyses

Examination of baseline characteristics will include estimates of the distribution of age, race, and other demographic characteristics, lab measures, and dialysis clinic. We will report baseline patient characteristics as counts (%) for categorical variables, and depending on the distribution, as means ± standard deviations (SDs) or medians [interquartile ranges] for continuous variables. Graphical methods including stem-and-leaf diagrams and boxplots will be used to examine distributions, identify potential influential points, and guide in the choice of transformations, if warranted.

6.3.4 Primary analyses (each assessed separately)

At designated study time-points, we will determine the [data type; see **Section 6.1** for definitions]:

- change from baseline for the short and longer-term efficacy measure [binary] (24-hour urine volume);
- value of short and longer-term safety electrolyte measures [binary] (serum potassium, magnesium, corrected calcium);

- value of serum furosemide levels [binary] (short and longer-term safety furosemide level measure);
- incidence of dialysis-associated hypotension [binary] (short and longer-term safety blood pressure);
- incidence of severe or very severe patient-reported allergic or toxicity-related symptoms [binary] (short and longer-term safety symptom measures);
- change from baseline of Inner EAR instrument score [binary] (short and longer-term safety symptom measure);
- incidence of severe or very severe patient reported symptoms [binary] (short and longer-term tolerability symptom measures);
- incidence of patient-reported acceptance of furosemide [binary] (short and longer-term acceptability measure);
- incidence of adherence by pill counts [binary] (short and longer-term adherence measure).

Change measures and value measures (e.g. 24-hour urine volume, serum electrolytes, serum furosemide level) will be analyzed via one-way repeated measures of analysis of variance to determine the presence of absence of dose-related differences. In addition, we will use mixed effects modeling to test the effect of increased dose and duration with the fixed effect of time (dose), random subject effect, and an unstructured repeated covariance type. We will use generalized estimating equations to assess categorical outcomes (e.g. sufficient increase in 24-h urine volume, hypokalemia, hypomagnesemia, hypotension, symptoms, Inner EAR score, patient acceptance). We will also consider binary outcomes as rates (events/time).

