6.1 Primary Endpoints

Short-term and longer-term efficacy- urine volume (assessed separately)

- Among participants with baseline 24-hour urine volume ≥200 mL: incidence of ≥25% increase in urine volume
- Among participants with baseline 24-hour urine volume <200 mL: incidence of a ≥50 mL increase in urine volume to a urine volume of at least 100 mL/24-hours

Short-term and longer-term safety- electrolytes (assessed separately)

- Incidence of serum potassium <3.2 mEq/L
- Incidence of serum magnesium <0.8 mg/dL
- Incidence of serum corrected calcium <7.0 mg/dL

Short-term and longer-term safety- furosemide levels

• Incidence of serum furosemide level >12 microgram/L

Short-term and longer-term safety- BP

 Incidence of dialysis-associated hypotension requiring hospitalization or treatment in an emergency room and not attributable to overt sepsis, acute myocardial infarction, or other cardiovascular event (e.g. aortic dissection)²¹

Short-term and longer-term safety- symptoms (assessed separately)

- Incidence of severe or very severe patient-reported rash, tinnitus, or hearing change) not attributable to causes
 other than furosemide
- Incidence of 10-point decrease in Inner EAR instrument score

Short-term and longer-term tolerability- symptoms (assessed separately)

• Incidence of severe or very severe patient-reported cramping, dizziness/pre-syncope, unusual tiredness/weakness, chest pain, nausea, vomiting, or diarrhea not attributable to causes other than furosemide

Short-term and longer-term acceptability

• Incidence of an affirmative response to the furosemide acceptance question

Short term- and longer-term adherence

• Incidence of participants having <20% of furosemide pills remaining at pill counts

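### Continuous measures have two analyses and no rule on which governs; the first-named, repeated-measures ANOVA, would use only complete cases if run classically

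*Combined protocol and SAP*

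**What the plan says.** Section 6.3.4 assigns change and value measures, with 24-hour urine volume, serum electrolytes and serum furosemide level as its examples, to "one-way repeated measures of analysis of variance", whose purpose is to establish whether there are differences by dose. The next sentence adds a mixed model with a fixed effect of time (dose), a random subject effect and an unstructured repeated covariance. A third sentence sends categorical outcomes to generalized estimating equations (GEE). The synopsis and section 6.3.5 repeat the same order of methods. No section says which of the ANOVA and the mixed model decides.

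On incomplete data, section 6.3.2 says "No imputation of missing data will be performed". Section 6.3.1 says "All analyses will be in intention-to-treat analyses" but defines no analysis set. Sections 4.5 and 6.3.2 ask participants who stop the drug to stay in follow-up.

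The primary efficacy endpoint in section 6.1 is a responder incidence, for example "Among participants with baseline 24-hour urine volume ≥200 mL: incidence of ≥25% increase in urine volume". Continuous changes in urine volume and electrolytes are exploratory in section 6.2. Yet section 2.1 calls 24-hour urine volumes the primary endpoint, and the power statement in section 6.4 concerns a mean change in urine volume.

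**The concern.** A classical one-way repeated-measures ANOVA needs a value from each participant at every level of the within-subject factor. With no imputation, a participant who misses one time-point leaves that analysis altogether. A mixed model fitted by likelihood keeps all observed values. The two analyses can therefore rest on different sets of people and disagree, with nothing in the plan to settle it.

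The losses need not be random. Visits take place at the outpatient dialysis clinic, so a hospitalised participant may miss them. Sections 1.3.1 and 9.2.1 provide for withdrawal from the study, including for adverse events or refused blood draws. The early-withdrawal visit in section 4.5 includes a 24-hour urine but lists no blood draw. If the factor is dose rather than week, the gap is built in: participants whose up-titration ends have no values at higher doses, and continued follow-up cannot supply them. That last route concerns the blood measures most, because only one post-baseline urine collection (week 5) falls in the escalation period.

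At stake are the estimates and intervals for the continuous measures and, where section 6.3.4 applies, their p-values.

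**Working it through.** **1. Reproduce the plan's own figure.** Section 6.4 gives n = 36, mean change 5 mL/24-h, SD of change 10, two-sided alpha 0.05. For a one-sample t-test on change, the noncentrality is (5/10) × √36 = 3 on 35 degrees of freedom, and power is 83.1%. The stated 83% reproduces.

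**2. Count the time-points.** Urine is collected at weeks -1, 5, 12 and 18: four. Blood is drawn at baseline and nine times after: ten. Section 4.1 and Table 2 place the last three draws at weeks 9, 13 and 17, and section 4.4 at weeks 10, 14 and 18. The count is the same.

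**3. Expected complete cases.** The documents give no missing rate, so m below is an assumption, taken as independent between visits. Expected complete cases are 36 × (1 − m)^k, with k = 4 for urine and k = 10 for blood.

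| m per visit (assumed) | Urine (1 − m)^4 | Complete of 36 | Blood (1 − m)^10 | Complete of 36 |
|---|---|---|---|---|
| 2% | 0.922 | 33.2, about 33 | 0.817 | 29.4, about 29 |
| 5% | 0.815 | 29.3, about 29 | 0.599 | 21.6, about 22 |
| 10% | 0.656 | 23.6, about 24 | 0.349 | 12.6, about 13 |

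**4. Vary the assumptions, at the same three rates.**
- Baseline always present (k = 3 and 9): about 34, 31 or 26 for urine and 30, 23 or 14 for blood.
- Period 1 alone (two urine collections, seven blood draws): 36 × (1 − m)^2 gives about 35, 32 or 29, and 36 × (1 − m)^7 gives about 31, 25 or 17.
- All 40 participants enrolled (k = 4 and 10): about 37, 33 or 26 for urine and 33, 24 or 14 for blood.
- Missing visits clustered in the same people would usually leave more complete cases than independence does.

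**5. What each method does with gaps.** One data set was simulated with 36 participants, four time-points and a nominal 10% missing after baseline. It held 127 of 144 values, so 17 of 108 post-baseline values were missing, and 21 participants were complete. A classical ANOVA routine refused the unbalanced data. A random-intercept mixed model kept all 36 participants and all 127 values, and GEE used all 127.

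**6. Can the planned mixed model be fitted as written?** An unstructured covariance over k times has k(k + 1)/2 parameters: 4 × 5/2 = 10 for urine and 10 × 11/2 = 55 for blood, the latter from about 36 participants. The unstructured matrix already absorbs the variance that a random subject effect would add, so including both is redundant at any k.

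**The case against.** The strongest reply is that the ANOVA is not the trial's primary analysis. The section 6.1 endpoints are incidences, every item in the section 6.3.4 list is tagged as binary, and GEE explicitly covers sufficient increase in urine volume. Section 6.3.5 forgoes p-values for exploratory measures, and section 6.3.1 puts the focus on estimates and intervals. That stands, and it limits the point to continuous measures. It does not remove the point, because section 6.3.4 itself places urine volume, electrolytes and furosemide level under the ANOVA.

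Three stronger readings are tempting, and the documents do not support them.
- A reader might infer that the plan drops anyone who misses a visit. No section says so. No software routine is named, a repeated-measures model can be fitted by likelihood, and declining to impute is not the same as choosing complete cases.
- A reader might infer an outright contradiction with intention-to-treat. The conflict arises only if the ANOVA is run classically, and it touches one of three methods. Stopping the drug does not by itself mean leaving follow-up.
- A reader might put the complete-case counts into the power formula, giving 73.9% at 29 or 65.0% at 24. The 83% belongs to a test that needs a baseline and one later value, not all four collections, and enrolment may reach 40.

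It may also be said that running both methods in a pilot is a matter of taste. But if the ANOVA is fitted by likelihood it largely duplicates the mixed model, and if it is classical it discards data. Neither case gives a reason to name it first.

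**Conclusion.** The point holds for continuous change and value measures. Two methods are named with no rule between them, and the first would be a complete-case analysis if run classically. The binary primary endpoints are untouched.

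The size is conditional. At the assumed 2% to 10% missing per visit, 33 down to 24 of 36 participants would have all urine collections, and 29 down to 13 all blood draws. Period-specific analyses would lose fewer. These figures rest on assumed, independent missing rates. The stated power reproduces and is not shown to be wrong. The plan should be changed because a better method is already in it and costs nothing to adopt. However, that mixed model cannot be made to govern exactly as written, because its covariance is over-parameterised.

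**What to change.** In the synopsis and sections 6.3.4 and 6.3.5:
- Remove the repeated-measures ANOVA, or keep it only as a descriptive check with its complete-case basis stated.
- Name the likelihood-based mixed model, using all observed time-points, as the governing analysis of continuous measures. In section 6.3.5 it would supply estimates and intervals only, as now planned.
- Specify the covariance. For the four urine times, use an unstructured matrix without the random subject effect. For the ten blood times, use a random subject effect or another structured covariance.
- Say whether the factor is week or dose.

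In section 6.3.1, define the intention-to-treat set and say how participants with missing visits enter each analysis. The mixed model relies on data being missing at random. It avoids discarding observed values but does not cure informative missingness, and section 6.3.7 lists no sensitivity analysis for missing data.

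The cost is wording only. Visits, sample size and data collection do not change, and one inferential analysis is removed.
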